#### Inclusion criteria

- Inpatients undergoing any surgical procedure not eligible for ambulant operation

- Operation performed at the Kantonsspital St. Gallen
- Patients hospitalised at the department of surgery at the Kantonsspital St. Gallen beginning from the starting day of the trial

#### Exclusion criteria

- Outpatients
- Patients who undergo operations at the hospital of Flawil or Rorschach but not at the Kantonsspital St. Gallen
- Patients operated by the department of surgery but hospitalized at any other department of the Kantonsspital St. Gallen

### **4.2 Recruitment, screening and informed consent procedure**

For quality control reasons, data from all operations performed by the department of surgery at the Kantonsspital St. Gallen are imported regularly from the operation management system (eOPPs) into the clinical database of the surgical department on a daily base. The database is already used to analyse morbidity and mortality on a daily base.

In this database, every added operation of all patients hospitalized after the starting date of the study will be screened electronically by a sql script if the inclusion- and exclusion criteria apply on a daily base. The result of the screening is documented in a sql table and depicted in the database by a special form, where the screening results are shown as read-only data.

Informed consent is not necessary because this study exclusively aims to optimize already quality control. No intervention interfering with the medical treatment is performed.

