## 3.2 Primary and secondary endpoints

### Primary endpoint

The primary endpoint is defined as the total reimbursement divided by the length of hospital stay including the entry and the demission day. Reimbursement per day was defined as the primary endpoint because it better reflects the ratio of costs and reimbursement in contrast to simple total reimbursement. When analysing the reimbursement in 2018, the distribution of total reimbursement per patient was extremely skewed. Hence, to achieve a reasonable power for statistical significance a high number of study participants would be needed.

The total reimbursement according to the DRG coding of each included patient will be provided by the financial department. At the end of the study the financial department will provide the total reimbursement for all included patients. The length of hospital stay of each patient will be extracted from the clinical database of the surgical department which is updated and monitored on a daily base. In cases of readmission within 18 days because of a related diagnosis the cases are aggregated.

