To support the process described above, for all patients randomized into the group with daily monitoring and optimization of DRG coding (treatment group), a pdf file with the current DRG grouping according to the procedures and diagnoses routinely coded in the Operation management software is created. Based on these procedures and diagnoses, the current DRG grouping status is estimated. Based on the estimated DRG grouping status, the actual length of stay is compared with the lower and upper limit and the mean length of stay determined by the associated actual DRG group. Additionally, based on routinely and systematically collected data in the clinical database of the surgical department, potential secondary diagnoses relevant for reimbursement are generated by computerized algorithms. For each potential secondary diagnosis, the hypothetical DRG Grouping considering the already coded procedures and diagnoses is estimated. The possible secondary diagnoses are deducted from laboratory measurements, from the extended Charlson comorbidity score routinely evaluated preoperatively by the department of anaesthesiology, and from the recording of perioperative complications.

Third, final discharge reports of patients randomized into the group with daily monitoring and optimization of DRG coding (treatment group), are controlled to ascertain the completeness of diagnoses and procedures and their concordance. Therefore, the electronic signature procedure of discharge reports will be adopted such that the report will not be sent before one of the dedicated physicians approved its final version.

In patients randomized into the control group none of the above described intervention steps will be performed. In these patients, the actual clinical routine will apply.

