## 4 STUDY POPULATION AND STUDY PROCEDURES

### 4.1 Inclusion and exclusion criteria, justification of study population

All patients undergoing any elective or emergency surgical procedure not eligible for ambulant operation at the Kantonsspital St. Gallen, Department of Surgery are eligible for study. All patients screened for the trial are documented in the screening log. Patients meeting the inclusion criteria are enrolled in the trial.

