#### Sample size calculation

Sample size calculation was performed in a separate simulation study using the total reimbursement divided by the length of hospital stay for the surgical department of the Kantonsspital St. Gallen in 2018. Sample size estimation was based on a two-sided significance level of  $\alpha = 0.05$  and a power of 90%. The increase in reimbursement was assumed to be 5% in the intervention group. Furthermore, in 15% of patients a shortening of the length of stay by one day was assumed in the intervention group. Randomization was 1:1. A drop-out rate of 10% was assumed. Based on this assumptions, a total of 1200 patients (600 per group) would be needed

to prove a significant increase in the total reimbursement divided by the length of hospital stay. According to the case load in 2018, the recruitment period would last 6 months.

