### **5.3. Randomization**

Randomization will be performed using the R sample function. 1:1 Randomisation will be performed in random block sizes of 4, 6 and 8. Randomisation will be performed automatically by the same sql script which is used for screening.

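### Could a re-operated patient be randomised twice, because screening runs per operation and the same script allocates?

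*Combined protocol and SAP*

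**What the plan says.** Screening is described at the level of the operation. Section 4.2 states that "every added operation of all patients hospitalized after the starting date of the study will be screened electronically by a sql script", on a daily basis. Section 5.3 links allocation to it: "Randomisation will be performed automatically by the same sql script which is used for screening". The list itself is conventional: "1:1 Randomisation will be performed in random block sizes of 4, 6 and 8".

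Eligibility is described at the level of the patient. Section 4.1 states that "Patients meeting the inclusion criteria are enrolled in the trial", and the first inclusion criterion is "Inpatients undergoing any surgical procedure not eligible for ambulant operation". No exclusion criterion in 4.1 mentions an existing allocation. The later exclusions in 4.3 and 4.4 concern only long stays beyond the end of recruitment and transfers to another department.

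The primary endpoint in 3.2 belongs to the hospital case: "In cases of readmission within 18 days because of a related diagnosis the cases are aggregated". For controls, 3.4 states that "In patients randomized into the control group none of the above described intervention steps will be performed".

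**The concern.** A patient who returns to theatre meets every inclusion criterion again, and the operation is a new row for the script. If the script drew a new allocation for each eligible row, two situations could arise.

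- **Same case.** A re-operation in the same stay, or an operation in a readmission that 3.2 merges with the first stay, could carry an allocation opposite to the first. One reimbursement, one length of stay and one discharge report would then belong to both arms. A control patient could be given daily monitoring, contrary to 3.4, and that exposure could not be undone at analysis.
- **Separate case.** A later or unrelated stay could enter as a further record for the same patient, possibly in the other arm. The Mann-Whitney test in 5.1 assumes independent observations.

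The plan does not say whether a doubly allocated case would be analysed under its first allocation, under both, or not at all. Re-operated patients plausibly stay longer, so the choice would affect a subgroup related to the outcome. At stake are a diluted contrast and an analysis rule chosen late.

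**Working it through.** **1. Which unit does the plan randomise?** The relevant places, side by side:

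| Place | Unit |
|---|---|
| 4.2, screening trigger | operation |
| 4.1, screening log and enrolment | patient |
| 3.4, both arms | patients randomised to a group |
| 3.2, primary endpoint | reimbursement and stay of each included patient, related readmissions merged |
| 3.2, readmission rate | readmissions checked against the randomisation list |
| 5.1, sample size | 1200 patients, 600 per group |
| 8.2, data recording | screening and randomisation results kept in a read-only table, in a database with an audit trail |

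Only the trigger is an operation. The readmission endpoint is the most telling entry: comparing readmissions by arm presupposes that a readmitted patient already has one identifiable allocation. The table in 8.2 means that an earlier allocation can be looked up, so a duplicate check is easy to implement.

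**2. The plan's own figure.** The 1200 comes from a simulation on 2018 data whose distribution is not given, so it cannot be reproduced. It is consistent with 540 evaluable patients per arm and 10% drop-out: 540 / 0.90 = 600. The 540 is inferred, not stated. The calculations below start from the stated 90% power at two-sided 0.05, for which the standardised effect is 1.960 + 1.2816 = 3.2415.

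**3. How often would a second draw disagree?** Within a block of size b the probability is (b/2)/(b − 1): 0.67, 0.60 and 0.57 for blocks of 4, 6 and 8. In a simulated list with these random block sizes, it is 0.58 for adjacent entries, 0.52 five places apart and 0.50 from ten places. With 1200 patients in 6 months, about 1200 / 180 = 6.7 are allocated per day, so a re-operation two or more days later is at least ten places away. I therefore use 0.50.

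**4. How many, and what loss?** Let q be the share of patients with a second eligible operation in the same case. The documents give no value; 2%, 5% and 10% are assumptions. Suppose that the script draws again and that a case is treated if either draw is intervention. Analysed by first allocation, a share q/2 of controls is treated, and

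power = Φ(3.2415 × (1 − q/2) − 1.96).

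If discordant cases are excluded instead, the contrast is kept but patients are lost:

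power = Φ(3.2415 × √(1 − q/2) − 1.96).

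| q | Drawn twice, of 1200 | Both allocations | Power, first allocation | Power, discordant excluded |
|---|---|---|---|---|
| 2% | 24 | 12 | Φ(3.2091 − 1.96) = 89.4% | Φ(3.2253 − 1.96) = 89.7% |
| 5% | 60 | 30 | Φ(3.1605 − 1.96) = 88.5% | Φ(3.2007 − 1.96) = 89.3% |
| 10% | 120 | 60 | Φ(3.0794 − 1.96) = 86.9% | Φ(3.1594 − 1.96) = 88.5% |

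With 0.58 in place of 0.50 at q = 10%, first-allocation power is Φ(3.2415 × 0.942 − 1.96) = 86.3%.

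**5. Least favourable handling.** Entering one record per allocation dilutes the effect by q/(1 + q): 2.0%, 4.8% and 9.1%. This was simulated with the Mann-Whitney test, 1080 evaluable patients, 12,000 replicates, and an assumed log-SD of 0.35 to 0.37 set to give about 90% power without repeats. Multi-operation cases were assumed to earn 30% less per day. Power went from 0.905 to 0.899, from 0.899 to 0.879 and from 0.899 to 0.857: losses of 0.6, 2.0 and 4.2 points. Rejection under the null was 0.047 to 0.052 under every handling rule.

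**The case for a change.** The best argument for acting is that allocation is automatic. The only operational account of screening names operations, and an implied unit is not an instruction to a script. A control patient wrongly drawn into the intervention cannot be made a clean control afterwards, and writing down a once-only rule costs almost nothing.

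Part of this stands: the rule is not written, and the documents do not show whether the script checks for an existing allocation. But the harm depends on the investigators building something at odds with how they describe enrolment, the randomised groups, the sample size and the readmission endpoint. A low cost of clarifying does not turn an unwritten detail into an error of design.

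Barring later, unrelated stays from the primary analysis as new records would go further, because it is a choice of analysis unit. Reimbursement arises per case, and 5.1 takes its recruitment forecast from cases: "According to the case load in 2018, the recruitment period would last 6 months". Including such stays with allowance for within-patient correlation would be equally defensible. Barring them has a price: if 5% to 10% of the 2018 load were repeat stays (assumed), recruitment would take 6 / 0.95 = 6.3 to 6.7 months (6 / 0.90).

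**Conclusion.** No change to the plan follows. The wording has a gap, since once-only randomisation is implied and not stated, but the patient-level text and the use of the randomisation list for readmissions point to one reading, which the investigators would almost certainly implement. No written rule produces a wrong result.

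If the script did draw again, the loss would be about 0.6 to 4 points of power for assumed repeat shares of 2% to 10%, depending on how discordant cases are handled, with type I error near 5%. Dilution of this kind makes a real effect harder to show; it does not create a false one. These sizes rest on three assumptions that the documents cannot confirm: the repeat share, a script without a duplicate check, and, for the simulated figures, the shape and spread of daily reimbursement.

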### **4.3 Study procedures**

The overall study duration is expected to be 7 months. The recruitment period is expected to be 6 months. Patients still hospitalized one month after the end of the recruitment period will be secondarily excluded.

### **4.4 Withdrawal and discontinuation**

Patients still hospitalized one month after the end of the recruitment period will be excluded. Patients who are initially hospitalized at the surgical department of the Kantonsspital St. Gallen and thereafter transferred to another department will be excluded from the analysis.

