### Secondary endpoints

1. Length of hospital stay: The number of days of the hospital stay including the entry and the demission day will be extracted from the clinical database of the surgical department
2. Total reimbursement per case: At the end of the study a list of included patients will be sent to the financial department. Based on this list, the financial department will provide the total reimbursement per case measured in Swiss Francs.
3. Case mix index: At the end of the study a list of included patients will be sent to the financial department. Based on this list, the financial department will provide the effective cost weight of each patient.
4. Severity of perioperative complications: The severity of perioperative complications are already routinely recorded applying the Clavien-Dindo-Classification. This standardized classification is chosen to ascertain external and internal comparability. Perioperative complications of all operated patients are routinely recorded by a dedicated physician and stored in the clinical database of the surgical department.
5. Readmission rate: On a daily basis, all admissions and readmissions are routinely presented and discussed during the morning meeting of the surgical clinic. The list of readmissions will be cross checked with the randomisation list and the demission of the included patients.

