## 3.4. Study intervention

First, based on the randomisation list, for all patients randomized into the group with daily monitoring and optimization of DRG coding (treatment group), dedicated physicians control if all relevant diagnoses and procedures are correctly coded in the operation management software. If necessary, additional codable diagnoses and procedures are discussed with the operating surgeon and if appropriate the coding is changed accordingly. Finally, the internal coherence of the coding and the wording of the operation report are crosschecked. Therefore, the electronic signature procedure of operation reports will be adopted such that the report will not be sent before one of the dedicated physicians approved its final version.

Second, the dedicated physicians control if relevant diagnoses and procedures are correctly recorded in the drafts of the discharge reports. Therefore, patients in the treatment group are visited daily. In addition, the patient records are inspected and their relevance for the DRG coding is assessed. If necessary, relevant diagnoses are incorporated in the draft of the discharge report. Additionally, the matching between diagnoses and procedures listed in the discharge report is crosschecked. The optimal time of discharge of each patient is evaluated on a daily base.

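### Randomised patients still in hospital one month after recruitment closes are excluded, so the analysis set is selected on length of stay; the likely effect is small, and avoiding it costs only a later data lock

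*Combined protocol and SAP*

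**What the plan says.** The rule appears twice. Section 4.4 (Withdrawal and discontinuation): "Patients still hospitalized one month after the end of the recruitment period will be excluded". Section 4.3 (Study procedures): "Patients still hospitalized one month after the end of the recruitment period will be secondarily excluded". The calendar comes from Section 4.3: "The recruitment period is expected to be 6 months" and "The overall study duration is expected to be 7 months", which leaves one month between the last entry and the cut-off.

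Screening runs electronically every day (Section 4.2), and the script that screens also randomises (Section 5.3). A patient caught by the rule has therefore already been allocated.

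Length of stay enters the trial in three ways:

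- Primary endpoint (Section 3.2): "The primary endpoint is defined as the total reimbursement divided by the length of hospital stay including the entry and the demission day".
- First secondary endpoint (Section 3.2): "Length of hospital stay: The number of days of the hospital stay including the entry and the demission day".
- Intervention (Section 3.4), in the treatment group only: "The optimal time of discharge of each patient is evaluated on a daily base". The sample size in Section 5.1 assumes a stay one day shorter in 15% of intervention patients.

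On readmissions, Section 3.2 says: "In cases of readmission within 18 days because of a related diagnosis the cases are aggregated". The financial department supplies reimbursement at the end of the study, and no extraction date is given.

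Section 5.2 specifies a complete case analysis. The plan gives no intention-to-treat set, no sensitivity analysis and no reporting of these exclusions by arm.

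**The concern.** For a given entry date, being in hospital at the cut-off is the same as having a stay above a threshold. The threshold is about 30 days for the last patient entered and about 210 days for the first. Two patients with the same 60-day stay are therefore treated differently: one who enters in month 2 is analysed, and one who enters in the last weeks of month 6 is removed.

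The selection happens after randomisation and depends on a quantity that the trial expects treatment to change. Randomisation then no longer guarantees that the analysed arms are comparable, and the trial is unblinded. The patients removed are also those who weigh most on any summary in means.

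The same calendar bears on the 18-day aggregation rule. If data were drawn at month 7, patients discharged in the preceding 18 days would not have had the whole window. A later related readmission would then go unaggregated, although the same event in an earlier patient would count.

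**Working it through.** **Inputs from the documents.** 1200 patients, 1:1; 6 months of recruitment plus 1 month; 10% drop-out; assumed effects of +5% reimbursement and one day less in 15% of intervention patients; Mann-Whitney test.

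**Inputs assumed.** Even enrolment, entry to the trial taken as the start of the stay, and lognormal stays. The 2018 data are named as the source for the sample size, but their distribution is not given.

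**The plan's own figure.** The total of 1200 comes from a simulation on those data and cannot be reproduced from the documents. The drop-out step is consistent with 540 analysable patients per arm: 540 / (1 − 0.10) = 600.

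**Patients excluded.** The entry rate is 1200 / 182.5 = 6.58 per day. With S(t) the probability of a stay longer than t days, the expected number excluded is 6.58 × ∫S(t)dt from 30 to 212.5 days.

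**Patients with an incomplete 18-day window, if data are drawn at month 7.** The expected number discharged in the last 18 days is 6.58 × [∫S(t)dt from 12 to 30 − ∫S(t)dt from 194.5 to 212.5].

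| Median stay, log-SD | Excluded | Share of 1200 | Discharged in last 18 days |
|---|---|---|---|
| 4 days, 0.8 | 6.58 × 0.059 = 0.4 | 0.03% | 6.58 × 0.483 = 3.2 |
| 5 days, 1.0 | 6.58 × 0.663 = 4.4 | 0.4% | 6.58 × 1.572 = 10.3 |
| 6 days, 1.1 | 6.58 × 1.734 = 11.4 | 1.0% | 6.58 × 2.511 = 16.5 |

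A wider grid (medians 4 to 8 days, log-SD 0.7 to 1.1) gives 0.1 to 21 excluded (0.01% to 1.7%). Among last-month entrants the share is 0.05% to 6.3%.

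**Who is lost.** In four scenarios checked, the excluded patients had mean stays of 50 to 108 days, against 6 to 15 days overall. At median 6, log-SD 1.1, the exclusion moves the median stay from 6.00 to 5.92 days and the mean from 10.99 to 10.15. At median 8, log-SD 1.1, the mean moves from 14.65 to 13.01.

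**Difference between arms under the Section 5.1 effect.** Shortening 15% of intervention stays by one day moves their threshold from 30 to 31 days. The expected difference in exclusions is 3.29 per day per arm × 0.15 × ∫S(t)dt from 30 to 31. The integrals are about 0.0055, 0.035 and 0.069, giving 0.003, 0.017 and 0.034 patients.

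**Effect on the primary test.** A simulation with 540 per arm, the Section 5.1 effects and an assumed reimbursement model gave these probabilities that an intervention value exceeds a control value, with and without the exclusion: 0.5355 and 0.5356 (median 5, log-SD 1.0), and 0.5330 and 0.5334 (median 6, log-SD 1.1). Power changed by less than 1 percentage point.

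**Worst case.** Suppose all k losses fall in one arm and all would have held the lowest ranks. The shift in z is (k × 540/2) / √(540² × 1081/12) = 270k / 5125, which is 0.11 for k = 2, 0.26 for k = 5 and 0.53 for k = 10. For scale, 90% power at two-sided 0.05 corresponds to an expected z of 1.96 + 1.28 = 3.24.

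**Readmissions actually affected.** The documents give no readmission rate. If 5% to 10% of the patients in the last column had a related readmission, at most 0.2 to 0.3, 0.5 to 1.0 and 0.8 to 1.7 patients would be affected in the three scenarios. The true number would be lower, because most of them have part of the window observed.

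**The case against.** The strongest defence is that the rule is an administrative calendar cut-off, identical in both arms, and that it removes a handful of patients. The loss sits inside the 10% drop-out allowance: losing even 25 patients takes power only from 90.0% to 89.3%. The plan tests stay and reimbursement by rank, so a few extreme values matter little. All of this stands, and it limits the size. It does not remove the selection, because a drop-out allowance protects power and not comparability.

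A reader might infer that the rule systematically deletes long control-arm stays and so materially biases the primary comparison. The documents do not support that. Under the plan's own assumed effect, the expected difference between arms is at most about 0.03 patients. It would be larger if the intervention acted mainly on very long stays, but the plan does not assume this.

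A reader might also add the two columns of the table and report up to about 2.3% of patients affected. That mixes patients who are removed with patients who are merely at risk of a changed value.

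Finally, a reader might infer that readmissions after month 7 are certainly ignored. The plan says only that data come at the end of the study. Under the synopsis, control-arm coding follows discharge, so final reimbursement must in any case come after the last discharges. The gap is an unstated extraction date, not a stated cut-off on readmissions.

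**Conclusion.** The concern holds as a design flaw of small expected size. Sections 4.3 and 4.4 remove randomised patients on a component of the outcome, and nothing else in the plan repairs it.

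The number lost is about 0.4 to 11 of 1200 (0.03% to 1%), consisting of extreme stays mostly among late entrants. Little effect is expected on the rank-based primary test. A visible effect is possible on mean stay if the tail is heavy; mean reimbursement could move too, but that was not calculated.

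The incomplete 18-day window is a separate and conditional matter. It concerns about 3 to 17 patients if data are drawn at month 7, of whom only those with a later related readmission would have a different value.

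All counts rest on assumed even enrolment and lognormal stays; the department's 2018 data would replace these assumptions. The change is still worth making, because stay and reimbursement come from routine databases and following these patients needs no extra contact.

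**What to change.** 1. Delete the exclusion of patients still in hospital from Sections 4.3 and 4.4. Close recruitment as planned and follow every randomised patient to discharge in the routine databases.
2. State an extraction date in Section 3.2: at least 18 days after the last discharge, and after final coding in both arms.
3. If a final cut-off date cannot be avoided, keep patients still in hospital in the length-of-stay analysis as censored at the accrued stay, using a rank test that accepts censoring, or rank them longest in a sensitivity analysis. Report their number by arm. For reimbursement per day, prespecify a sensitivity analysis that gives them the lowest rank.
4. Do not fill in reimbursement for these patients from an interim DRG grouping. Section 3.4 provides a running grouping only in the treatment group, while the synopsis has control patients coded after discharge. Interim values would be measured differently in the two arms.

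The cost is a change of wording and a database lock some weeks later. The sample size does not change, and no patient contact is added.

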Study Intervention	In the intervention arm, reporting and the time of demission are crosschecked and corrected by physicians with special awareness of the DRG system during the hospital stay (preliminary precoding).
Control Intervention	In the control arm the coding for DRG grouping is performed after the patient's demission. Reports are not screened for conformability to the DRG coding system.
Study procedures	In the intervention arm, reporting and the time of demission are crosschecked and corrected by physicians with special awareness of the DRG system during the hospital stay (preliminary precoding).
Study Duration and Schedule	Planned 06/2019 of First-Participant-In Planned 01/2020 of Last-Participant-Out
Investigator	[name], Department of Surgery, Kantonsspital St. Gallen, St. Gallen, Switzerland E-mail: [contact] [contact]

Study Centre(s)	Kantonsspital St. Gallen, St. Gallen, Switzerland
Data privacy	No additional data exceeding the routine clinical data are generated. The electronic processing of these routine clinical data will be performed in the clinical database of the surgical department which is password-protected. As an additional measure of data privacy, only physicians involved in the study will be granted access to the results of electronic data processing.
Ethical consideration	The intervention assessed in this study consists of measures of quality control based on the DRG grouping. All data used for this study are already available to every physician involved in the treatment. For patients who are in the treatment group, treatment and reports are more extensively controlled by physicians. Thus the risk to overlook faults in documentation or treatment is likely to be reduced. If a more close implementation of the DRG Grouping transfers into less severe morbidity, a potential benefit for the participant would result.
GCP Statement	This study will be conducted in compliance with the protocol, the current version of the Declaration of Helsinki, the ICH-GCP, the HRA as well as other locally relevant legal and regulatory requirements.

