## 3.3 Study design

This is a monocentric, randomised two-arm un-blinded study.

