### **5.2. Handling of missing data and drop-outs**

In case of missing data and drop-outs a complete case analysis is performed.

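### Patients transferred or still in hospital at the cut-off are dropped after randomisation, with no all-randomised analysis and no report of exclusions by arm

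*Combined protocol and SAP*

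**What the plan says.** Section 4.2 describes a daily electronic screen of every newly imported operation. Section 5.3 adds: "Randomisation will be performed automatically by the same sql script which is used for screening". Allocation therefore happens soon after the operation is imported, while the rest of the hospital course is still open.

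Two rules then remove patients who have already been allocated:

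- Section 4.4: patients first admitted to surgery and "thereafter transferred to another department will be excluded from the analysis".
- Section 4.3, repeated in section 4.4: "Patients still hospitalized one month after the end of the recruitment period will be secondarily excluded".

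Section 5.2 adds: "In case of missing data and drop-outs a complete case analysis is performed". Section 5.1 names the tests but defines no analysis set.

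On design, section 3.3 states: "This is a monocentric, randomised two-arm un-blinded study". According to the synopsis, in the intervention arm "reporting and the time of demission are crosschecked and corrected by physicians with special awareness of the DRG system". Section 3.2 defines the primary endpoint as reimbursement divided by length of stay. On the numerator it says: "At the end of the study the financial department will provide the total reimbursement for all included patients". On the denominator: "The length of hospital stay of each patient will be extracted from the clinical database of the surgical department".

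**The concern.** Randomisation makes the arms comparable at allocation. A rule that removes patients because of something that happens later keeps that comparability only if it removes the same number and the same kind of patient from each arm. Here staff know the allocation, and one arm receives daily review that includes discharge timing.

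The two rules are not equally exposed. For patients still in hospital at the cut-off, the link to length of stay is definitional, but the group is probably small. For transfers, an effect of the intervention is only a plausible inference: the documents give no reason, timing or count of transfers, and do not say that the intervention affects them.

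The direction is open. If the intervention leads to fewer exclusions of patients with low reimbursement per day, the bias works against it; if it leads to more, the bias favours it. Section 4.4 does not limit the transfer rule to the primary endpoint, so as written it also reaches complications and the readmission safety endpoint.

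**Working it through.** **The plan's own figure.** Section 5.1 gives 600 per arm with a 10% drop-out allowance. This fits 540 analysable per arm: 540 / (1 − 0.10) = 600, and 2 × 600 = 1200. The simulation on 2018 data behind the 540 is not shown, so it cannot be reproduced. The allowance protects precision, not comparability, and the plan does not say what share of it these exclusions account for.

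**Imbalance implied by the plan's stay assumption.** Section 5.1 assumes one day less in 15% of intervention patients, an average of 0.15 × 1 = 0.15 day. Assume a mean stay of 4 to 8 days and, in control, 10% excluded in proportion to stay. The difference between arms is then 10% × 0.15/8 = 0.19 points to 10% × 0.15/4 = 0.38 points.

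**Cut-off rule alone.** With assumed log-normal stays (median 5–9 days, log-SD 0.8–1.0) and uniform entry over six months, about 0.5 to 9 of 600 patients per arm are lost. The planned shortening changes this by less than 0.1 patient per arm. Any material problem would come from transfers.

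**Illustration of unequal exclusion, no true effect.** All inputs are assumed: 600 per arm, log-SD 0.4, and exclusions drawn only from a quarter of patients whose reimbursement per day is 33% or 50% lower.

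If a fraction *e* of an arm is excluded, the low-value share among those left is (0.25 − *e*)/(1 − *e*). The shift in log reimbursement per day is the difference in that share (intervention minus control) times ln(0.67) = −0.40 or ln(0.50) = −0.69. For 9% intervention against 11% control:

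- intervention: 0.16/0.91 = 17.6%; control: 0.14/0.89 = 15.7%; difference about 1.85 points
- shift: 0.0185 × (−0.40) ≈ −0.7%, to 0.0185 × (−0.69) ≈ −1.3%

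For the imbalance of 0.19 to 0.38 points, the same formula gives a shift of about −0.1% to −0.2%.

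Simulated Mann-Whitney tests (two-sided 5%, 20,000 trials per setting; ranges cover the 33% and 50% cases):

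| Excluded, intervention / control | Two-sided error | False benefit (nominal 2.5%) | Shift |
|---|---|---|---|
| 10% / 10% | 5.0–5.1% | – | 0 |
| 9.8% or 9.63% / 10% | 4.8–5.2% | – | −0.1% to −0.2% (formula) |
| 9% / 11% | 5.9–6.8% | 0.9–1.3% | −0.7% to −1.3% |
| 11% / 9% | 5.9–7.3% | 4.7–6.2% | +0.7% to +1.3% |
| 8% / 12% | 8.6–13.0% | 0.3–0.6% | −1.5% to −2.5% |
| 12% / 8% | 8.7–13.2% | 8.0–12.9% | +1.5% to +2.6% |

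Nothing in the documents supports imbalances as large as those in the last two rows; they only show how the error grows.

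Equal counts are not a safeguard. With 5% excluded in each arm, at random in the intervention arm but entirely from the low quarter in control (an extreme case), the error is 9.4–14.9% and the shift −1.6% to −2.7%. Exclusion unrelated to outcome leaves the error near 5%. Error rates are somewhat lower if the low-value group is fixed at 150 per arm instead of varying by chance; the pattern is the same.

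**Power cost of keeping transferred patients.** Same model, effect set for about 90% power; the two values per cell are the 33% and 50% cases.

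| Transferred, effect they receive | Power with exclusions | Power, all randomised | Change (points) |
|---|---|---|---|
| 5%, half | 0.908, 0.891 | 0.904, 0.879 | −0.4, −1.2 |
| 5%, none | 0.910, 0.894 | 0.893, 0.870 | −1.7, −2.4 |
| 10%, half | 0.902, 0.896 | 0.891, 0.864 | −1.1, −3.2 |
| 10%, none | 0.903, 0.896 | 0.858, 0.835 | −4.5, −6.1 |
| 10%, full | 0.904, 0.897 | 0.920, 0.894 | +1.6, −0.3 |

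**The case against.** The best defence is that no bias is shown. The only scenario tied to a figure in the plan leaves the error at its nominal level; every inflated rate rests on an assumed imbalance, an assumed low-value group and an assumed SD. This stands. The illustration shows what could happen, not what is likely.

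Second, the transfer rule has a coherent purpose. The eligibility criteria in section 4.1 already exclude patients who are operated on by surgery but hospitalised in another department, so the rule may aim at one target population. After a transfer, delivery of the intervention and completeness of the recorded stay are uncertain. This also stands as a motive. But an eligibility criterion applied at entry cannot be affected by the allocation, whereas a rule applied afterwards can.

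Third, section 4.2 says that nothing in the study interferes with medical treatment, and discharge timing is not inter-department transfer. So the documents do not establish that the intervention changes transfers. They do not rule it out either, and the plan contains no step that would reveal it.

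Fourth, the remedy may not be fully feasible. Stay comes from the surgical department's database, and dividing whole-case reimbursement by a surgery-only stay would distort the ratio. Including transferred patients can also cost power. Both points stand and shape the fix. The complete-case rule in section 5.2 probably adds little beyond the two explicit exclusions.

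**Conclusion.** The concern holds. It is certain from the text that both exclusions act after allocation and that the plan offers no all-randomised analysis, sensitivity analysis or report of exclusions by arm. Whether this biases the result, by how much and in which direction cannot be determined from the documents, because transfer rates and the outcomes of transferred patients are not given.

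Under the plan's own stay assumption the effect is negligible. Under an assumed difference of two percentage points between arms, with exclusions drawn from patients with low reimbursement per day, reimbursement per day shifts by about 0.7–1.3% either way. That is not trivial beside the 5% increase in reimbursement the trial is sized on. The cut-off rule is a minor part; transfers are the main issue. This should be fixed because the remedy is cheap and guards against an otherwise undetectable problem, not because bias has been demonstrated.

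**What to change.** 1. Define the primary analysis set as all randomised patients, analysed as allocated.
2. For transferred patients, use whole-case reimbursement and whole hospital stay, after confirming that days after transfer can be obtained from hospital or finance records.
3. For patients still in hospital at the cut-off, collect reimbursement and stay after discharge.
4. Keep the analysis with the current exclusions as a sensitivity analysis.
5. Report exclusions by arm and reason.
6. If stay after transfer cannot be retrieved, say so and still report transfers by arm.

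The cost is SAP wording, a somewhat later data request and one check of data availability. Power may fall: by about 0.4 to 2.4 points in the model above if 5% are transferred and receive half or none of the effect, and by up to about 6 points if 10% are transferred and receive none.
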